13.4.2 Secondary Efficacy Analysis

The secondary efficacy objectives will be analysed using the same principles and methods as the primary efficacy objectives.

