6.2 Secondary Objectives

- To describe and compare the ability of Lumentin® 44 to fill the bowel as compared to Movprep® and diluted Omnipaque®.
- To describe and assess how Lumentin® 44 influences reading of the abdominal CT-examination as compared to Movprep® and diluted Omnipaque® with respect to:
 - Diagnostics with particular regard to parenchymal organs, lymphatic system and tissue compartments beyond the gastrointestinal tract
- To investigate signs of degradation of Lumentin® 44 in terms of
 - Coalescence
 - Syneresis or drainage
- Describe and compare the ability to eat/drink for each of three contrast agents with respect to:
 - Taste
 - Smell
 - Consistency
 - Ability to swallow
 - Fullness
- Validity and repeatability of the primary endpoint
- To evaluate safety and tolerability after oral administration of each of three contrast agents

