7.2.2 Secondary Efficacy Variables

- Bowel filling properties (extension and distension) on Abd-CT in each of 5 selected sub-segments of the small bowel
- Degradation (presence of bubbles and signs of sedimentation) on Abd-CT in each of 5 sub-segments of the small bowel
- Diagnostic ability on Abd-CT of the parenchyma, lymphatic system and tissue compartments beyond the gastrointestinal tract.
- Subject assessments of taste, smell, consistency, ability to swallow and fullness after swallowing the contrast agent

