9.5 Drug Accountability

The Investigator is responsible for maintaining accurate investigational product accountability records throughout the trial.

Each dispensing of investigational product will be documented in the drug accountability log and the eCRF.

The height of the Lumentin® 44 foam in the PET jar will be measured prior to dispensing it to the subjects. The weight of all three contrast agents will be measured prior to dispensing as well as after intake. Height and weights will be and noted in the eCRF. Drug accountability will be carried out at regular intervals, as specified in the monitoring plan.

All unused investigational product (Lumentin® 44 dispersion) will be returned to Bioglan AB for destruction at the end of the trial. The Sponsor will be provided with the documentation of destruction of unused investigational product.

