10.1.5 Ability to eat/drink the contrast agents

Subjects will assess taste, smell, consistency, ability to swallow and fullness on a five degree-scale:

6. Very negative/Very difficult/very full
7. Negative/difficult/ full
8. Neutral/medium/medium full
9. Positive/easy/barely full
10. Very positive, good/very easy/not at all full.

Subjects will be handed an assessment form, see appendix 2, to be filled out during the period when the contrast agents are consumed.

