13.1.2 Protocol Deviations

Deviations to the trial protocol will be documented in a Protocol Deviation Log.

Deviations from the protocol including violations of inclusion/exclusion criteria will be assessed as “minor” or “major” on a case-by-case basis in cooperation with the Sponsor. This assessment will take place during a data review meeting. Major deviations from the protocol will lead to the exclusion of a subject from the per protocol analysis set.

Unless decided otherwise during the data review meeting, the following will be major protocol deviations:

- Deviations of inclusion/exclusion criteria,
- Subjects not able to drink at least 750 mL Lumentin® 44
- Subjects not able to drink at least the, according to the general praxis of care, recommended dose of diluted Omnipaque®
- Subjects not able to drink at least the, according to the general praxis of care, recommended dose of Movprep®

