13.1.3 Analysis Populations

Safety set:	All subjects who received at least some portion of the contrast agents (Lumentin® 44, diluted Omnipaque® and Movprep®). Subjects will be included in the analysis according to the treatment actually received.
Full analysis (FA) set:	All correctly included and randomised subjects who received at least some portion of the contrast agents (Lumentin® 44, diluted Omnipaque® and Movprep®) and for whom a CT-scan has been performed. All subjects will be included in the group according to the intention based on the randomisation.
Per protocol (PP) set:	All subjects of the FA set who are compliant with the trial protocol, i.e., who do not experience any major protocol deviations.

All efficacy analyses will be performed for both the FA set and the PP set. The analysis of the primary efficacy parameter based on the PP set will be regarded as the primary analysis. The analyses on the FA set will be considered as sensitivity analyses.

All safety analyses will be based upon the Safety Set.

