13.4 Efficacy Analyses

The primary efficacy objective will be analysed using data from patients in both the FA set and the PP set considering the results from the PP set as the primary results.

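### The lead comparison of how drinkable the three agents are leaves out the subjects who could not drink the required volume

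*Combined protocol and SAP*

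**What the plan says.** Section 6.2 sets as a secondary objective: "Describe and compare the ability to eat/drink for each of three contrast agents with respect to" five attributes, and Section 7.2.2 makes the ratings a secondary efficacy variable. Section 10.1.5 defines them: "Subjects will assess taste, smell, consistency, ability to swallow and fullness on a five degree-scale". It has no grade or rule for a subject who stops early.

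On analysis, Section 13.4.2 states: "The secondary efficacy objectives will be analysed using the same principles and methods as the primary efficacy objectives". Section 13.4 uses both sets for the primary objective, "considering the results from the PP set as the primary results", and Section 13.1.3 makes FA a sensitivity analysis. PP is FA without major deviations. The default major deviations in Section 13.1.2 include "Subjects not able to drink at least 750 mL" of Lumentin, or the recommended volume of either comparator. FA takes correctly included, randomised subjects who received some of the agent "and for whom a CT-scan has been performed".

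Three other places bear on the point:

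- Section 7.1 removes subjects below the minimum from all efficacy evaluations, which is stricter than Section 13.1.3.
- Section 8.3 requires them to be withdrawn, but adds that the clinic normally scans them anyway.
- Appendix 2 lets taste, smell and consistency be rated while drinking, but asks subjects to hold the drinkability and fullness ratings until they leave for X-ray.

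**The concern.** Failure to get the volume down is the most direct evidence that an agent is hard to drink. If those subjects are set aside as protocol violators, the lead comparison asks only how the subjects who managed it rated the agent. Randomisation does not protect that comparison, because the selection happens after treatment starts and may differ by arm. The required volumes also differ: at least 750 mL for Lumentin, and the department's recommended volume for each comparator.

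At stake is a stated comparative objective. Two agents with similar ratings among finishers could differ in how many subjects finish, and no planned drinkability comparison would count that difference.

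**Working it through.** **1. The plan's own figure.** The documents give no figure for the drinkability analysis. The nearest is the 78% power per primary comparison in Section 13.6.1. With 40 v 20, difference 1.50 and SD 2.00, z = 1.50 / (2.00 × √(1/40 + 1/20)) = 2.74, and power = Φ(2.74 − 1.96) = 78.2%. It reproduces. The present point does not depend on it.

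**2. Tracing the analysis set.**

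- The ratings are secondary efficacy variables (6.2, 7.2.2).
- Secondary objectives follow the primary's principles (13.4.2).
- Those principles make PP lead and FA a sensitivity analysis (13.4, 13.1.3).
- PP drops subjects below the minimum volume unless the data review meeting decides otherwise (13.1.2).

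The lead set for ability to drink is therefore restricted by ability to drink.

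**3. What the restriction can hide.** All rates and rating distributions here are assumptions. Finishers rate swallowing alike in both arms, with probabilities 0.03, 0.12, 0.35, 0.35 and 0.15 for grades 1 to 5. Their mean is 0.03 + 0.24 + 1.05 + 1.40 + 0.75 = 3.47, and 15% give grade 1 or 2. A share f of the Lumentin arm fails the minimum and rates 1 (70%) or 2 (30%), mean 1.3. All comparator subjects finish, and every failure supplies a rating.

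Mean over all starters = (1 − f) × 3.47 + f × 1.3. Share at grade 1 or 2 = (1 − f) × 0.15 + f. Rejection rates are simulated with the two-sided 5% Wilcoxon rank sum test at 44 v 22 (88 subjects split 2:1:1), with 3,000 or 4,000 trials per case. The ranges cover repeated runs.

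| f | Mean, all starters | Grade 1 or 2 | Rejection, all starters | Rejection, PP |
|---|---|---|---|---|
| 8% | 3.30 | 22% | 7–8% | about 5% |
| 15% | 3.14 | 28% | 14% | about 5% |
| 25% | 2.93 | 36% | 33–35% | about 5% |

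In PP the Lumentin arm shows 3.47 and 15% at every f.

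**4. A second set of assumptions.** Finisher probabilities are 0.05, 0.15, 0.30, 0.35 and 0.15, failures count as the worst grade, and the comparison is 40 v 20. At f = 8% the mean difference is −0.20 grade with 6% rejection; at 20% it is −0.47 with 21%; at 26% it is −0.62 with 34%. PP stays near a zero difference, with 4 to 5% rejection.

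**5. Anchoring f.** Section 7.3.2 reports that 23 of 25 pilot subjects drank more than 0.9 L, so 2/25 = 8% did not (exact 95% interval 1.0% to 26.0%). That was at a higher threshold and, per Section 5.2, with a 60% air foam. It is only a rough guide to failure at 750 mL of the 44% air foam.

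**6. Failures in both arms.** With 8% failing in each arm, rejection is below 5% in both analyses. Ratings in each arm are then overstated, but the comparison hardly moves.

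**The case against.** The best defence has four parts.

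- **FA already holds most of these subjects.** A reader might infer that those who give up disappear from both sets. The documents do not support that: Section 8.3 says the scan is normally done anyway, so under Section 13.1.3 most non-finishers are in FA, and efficacy is analysed in both sets. This stands, but FA is only a sensitivity analysis, and Section 7.1 read literally removes them there too.
- **Failures are reported.** A reader might also infer that inability to drink goes unreported. Withdrawal reasons are summarised with disposition (13.1.1), and the amount taken is summarised by arm (13.4.3). This stands as description. Neither is a drinkability comparison.
- **PP primacy for secondary variables is inferred.** The explicit sentences name only the primary objective and parameter, and the data review meeting may reclassify deviations. Both are true. Yet Section 13.4.2 carries the principles over, no section names another lead set, and case-by-case reclassification in an open trial is not a safeguard.
- **The effect may be slight.** At 8% in one arm it is. The 15% and 25% cases exceed the 10% dropout allowed for in Section 8.4. This stands: the larger figures show sensitivity and are not a forecast.

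**Conclusion.** The point holds. As written, the lead analysis of the five ratings excludes those who could not drink the minimum, so it is conditioned on the outcome it is meant to compare. The set that would keep most of them is secondary, and Sections 7.1 and 13.1.3 disagree on whether they belong in it.

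The size is unknown because no failure rate at 750 mL is given. Under the assumptions shown, the test is barely affected at about 8% failing in one arm and clearly affected at 15% to 25%. It is tempting to conclude that the plan flatters Lumentin. The documents do not support this: comparator subjects face their own minimum, which may be harder or easier to reach, so the direction is open. The flaw in the choice of set does not depend on the rate. It concerns secondary ratings and cannot change the primary conclusion.

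**What to change.** 1. In Section 13.4.2, name all randomised subjects who took any portion of the agent, scanned or not, as the lead set for the five ratings, analysed by randomised arm, with PP supportive. The ratings do not need a CT.
2. In Section 10.1.5 and Appendix 2, have the form completed when drinking stops, including by those who stop early. Changing the set alone would not recover ratings deferred until the subject leaves for X-ray, because Section 13.2 allows no substitution of missing values.
3. Report the proportion not reaching the required volume by arm with Fisher's exact test, stating that the required volume differs between arms.
4. Reconcile Section 7.1 with Section 13.1.3 on whether subjects below the minimum enter efficacy analyses.

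The container weights (Section 9.5: "The weight of all three contrast agents will be measured prior to dispensing as well as after intake") may suggest the fraction of dispensed mass as an outcome. It should not be compared between arms: Lumentin has a permitted range of 750 to 1200 mL and the comparators a practice volume, so a compliant Lumentin subject could score well below 1.

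The cost is SAP wording plus minor protocol wording, with no new visits or measurements. The downside is that ratings in any arm with non-finishers may look less favourable.

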13.4.3 Drug Exposure

Extent of exposure will be assessed using the amount contrast agent taken and body weight. The total exposure and exposure divided by the subject's body mass index will be summarised by treatment group using descriptive statistics.

13.4.4 Validity and repeatability of the primary endpoint

The primary endpoint (i.e. the contrast) will be assessed by both the investigator and the sub-investigator, independently of each other. As an exploratory analysis, the relationship between the contrast measurements done by the investigator and the sub-investigator will be analysed. The relationship will be investigated by calculating the Spearman rank correlation coefficient. As an analysis of a systematic difference between the operators the hypothesis that the contrast level is equal for the investigator and the sub-investigator will be tested using the Wilcoxon signed rank test.

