8.4 Planned Sample Size and Number of Trial Centres

It is planned to randomise 40 evaluable subjects to the Lumentin arm and 20 subjects to each of the Omnipaque and Movprep arms. To cover for a 10% drop out rate a total of 93 subjects will be randomised.

Randomisation will be terminated when 40:20:20 evaluable subjects are reached in respective arm. See Section 13.6 for a discussion of sample size.

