8.5 Subject Identification and Randomisation

Subjects referred to CT examination of the abdomen will receive an invitation to the CT examination by letter. An advertisement letter informing about the trial will be included in this referral letter.

All referrals for abdominal CT are read and prioritized by the investigator/sub-investigator. Those subjects, irrespective from which medical clinic, who the radiologist think are possible candidates for the trial, will have the advertisement letter added to the referral letter sent home to them with date and time for their CT-examination.

An invitation log will be kept with names of those receiving the advertisement letter. Subjects will subsequently be contacted by and asked if they are interested in participation. Those interested will be sent the subject information leaflet.

All subjects receiving the patient information leaflet will receive a screening number consisting of S followed by three digits: S-XXX starting with S-101.

The Investigator will allocate the screening numbers in ascending order.

Enrolled subjects who drop out of the trial before randomisation will retain their screening number.

Randomisation will occur at the clinic on the day of examination when all screening procedures have been performed and eligibility for the trial confirmed. Each randomised subject will receive a unique randomisation number consisting of R followed by three digits: R-XXX starting with R-101. Randomisation numbers will be allocated in strict ascending order according to a randomisation list

Randomised subjects who terminate their trial participation for any reason, regardless of whether trial drug was taken or not, will retain their randomisation number.

Subjects will be randomised on a 1:1:1 basis to Lumentin® 44, diluted Omnipaque® or Movprep®. The randomisation will be in blocks and stratified by gender as the drinking capacity differs between males and females.

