13 STATISTICAL METHODS

Before disclosure of randomisation codes, a separate statistical analysis plan (SAP) may be finalised, providing detailed methods for the analyses outlined below.

In general, data summaries will be stratified by the randomised treatment group (Lumentin® 44, diluted Omnipaque® and Movprep®). The randomisation is stratified by gender and this will be taken into consideration in the statistical analyses

Any deviations from the planned analyses will be described and justified in the final integrated trial report.

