13.6 Determination of Sample Size

13.6.1 Sample size (per group)

The standard deviation of the primary variable (i.e. the difference in contrast density in HU between bowel lumen and wall (mucosal lining), expressed as the mean of 9 measurements performed in the 5 selected sub-segments of the small bowel) is estimated from the first pilot clinical study of abdominal CT examinations on healthy volunteers using a slightly different formulation (L60). Based on data from that study [1] it is assumed that the standard deviation will be around 2.00 and the difference between Lumentin® 44 and Omnipaque® as well as the difference between Lumentin® 44 Movprep will be 1.50. Then 40 fully evaluable patients in the Lumentin group and 20 patients in each of the comparator groups are needed to get 78 % power for each of the two primary objectives (no adjustment for multiplicity). This means that the total probability in the trial to get a p-value less than 5 % in the test of both the primary objectives is $0.78 \times 0.78 = 0.61$.

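### Section 13.4.4 plans no measure of how far apart the two readers are in HU, and does not say whether the reader correlation is pooled or by arm

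*Combined protocol and SAP*

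**What the plan says.** Section 6.2 lists "Validity and repeatability of the primary endpoint" among the secondary objectives. The only analysis that serves it is in section 13.4.4, which opens: "As an exploratory analysis, the relationship between the contrast measurements done by the investigator and the sub-investigator will be analysed". The method follows: "The relationship will be investigated by calculating the Spearman rank correlation coefficient". For a systematic difference, "the hypothesis that the contrast level is equal for the investigator and the sub-investigator will be tested using the Wilcoxon signed rank test".

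The section names no limits of agreement, no intraclass correlation and no acceptance threshold. It does not give the unit of analysis (subject mean or single ROI), and it does not mention treatment arm. The nearest guidance is the general rule in section 13, "In general, data summaries will be stratified by the randomised treatment group", which is not tied to the reader coefficient.

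Under section 10.1.1 each reader chooses images and ROI sites separately and contributes up to nine values. The wall is fixed at +80 HU for both readers, and the endpoint averages all measurable values from both.

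Arm sizes are given in two ways. Section 8.4 has "Randomisation will be terminated when 40:20:20 evaluable subjects are reached in respective arm", and section 8.5 has "Subjects will be randomised on a 1:1:1 basis to Lumentin® 44, diluted Omnipaque® or Movprep". In section 13.6.1 "it is assumed that the standard deviation will be around 2.00", with a difference of 1.50 from each comparator. No unit is attached to either figure.

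**The concern.** A repeatability objective asks how closely two readers agree on the same subject, in the units of the measurement. A rank correlation asks only whether they order the subjects alike. A signed rank test asks only whether one reader tends to be higher. Two readers could differ widely and at random on every subject and still give an unremarkable result on the second test.

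The unstated grouping adds a further risk. If the coefficient is computed across all three agents, part of it reflects the gap between agents and not reader agreement. The background in section 5 describes a wide gap: foam down to -600 HU against about 10-20 HU for neutral agents. Section 7.3.1 likewise reports a large lumen-to-wall difference with the foam.

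This is the plan's only check on a measurement with considerable reader freedom, because ROIs go where the lumen shows best. A high coefficient could be taken as support for that freedom without agreement having been measured.

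**Working it through.** **1. The plan's own figures.** The documents give no figure for reader agreement. The only numerical planning inputs are in section 13.6.1: difference 1.50, SD 2.00, 40 against 20 subjects, two-sided 5%.
- Separation: 1.50/2.00 = 0.75 SD.
- Power (normal approximation): 0.75 × √(40×20/60) − 1.96 = 2.739 − 1.960 = 0.779, which gives 0.782. The stated 0.78 reproduces, as does 0.78 × 0.78 = 0.61.

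**2. What Spearman misses.** An increasing linear change in one reader's values leaves all ranks unchanged. Suppose the second reader's value is 1.3 times the first plus 50. For illustration, a lumen at -600 HU gives a contrast difference of -600 − 80 = -680. The second reader then has 1.3 × (-680) + 50 = -834, which is 154 HU away, and Spearman is still 1.00. This holds pooled or by arm.

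**3. What the signed rank test misses.** If reader differences are symmetric about zero, the test rejects at its nominal rate however wide they are. In simulated 40:20:20 data with zero within-arm reader correlation and no mean shift, it rejected in 4.3% to 6.0% of runs across the settings below. In those data the reader difference has SD √2 times the within-arm SD. Limits of agreement would therefore show ±1.96 × √2 = ±2.77 within-arm SDs.

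**4. Spearman if pooled, with zero within-arm correlation.** With fully separated groups of size n_g and total N, the expected value is 1 − Σ(n_g³ − n_g)/(N³ − N), where 80³ − 80 = 511,920.
- Three separated arms, 40:20:20: 1 − (63,960 + 7,980 + 7,980)/511,920 = 1 − 79,920/511,920 = 0.84.
- Comparators overlapping, 40:40: 1 − (2 × 63,960)/511,920 = 1 − 127,920/511,920 = 0.75.

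Partial separation, comparators overlapping (normal data, equal SDs, 1,000 runs per row):

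| Separation (SD) | Mean pooled Spearman | 95% range |
|---|---|---|
| 0.75 (the plan's ratio) | 0.123 | -0.074 to 0.323 |
| 1 | 0.201 | -0.024 to 0.400 |
| 1.5 | 0.380 | 0.178 to 0.555 |
| 2 | 0.535 | 0.371 to 0.672 |
| 3 | 0.703 | 0.618 to 0.782 |
| 5 | 0.749 | 0.692 to 0.802 |
| 10 | 0.749 | 0.698 to 0.800 |

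Within the Lumentin arm the same data give about 0.00 throughout. At 10 SD, a within-arm Pearson correlation of 0.3 (within-Lumentin Spearman 0.28) appears as 0.82 pooled, and 0.6 (0.57) appears as 0.89.

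**5. Allocation.** Under 1:1:1 (27:27:26) the two full-separation values become 0.89 (three arms) and 0.67 (comparators overlapping). The conflict between sections 8.4 and 8.5 changes the figures but not the conclusion.

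**6. Which row applies.** This cannot be settled from the documents, because no within-arm SD is stated in HU. Taking -600 and +20 HU at face value, the gap is 620 HU. It reaches 5 SD only if the within-arm SD is at most 620/5 = 124 HU. At half that gap the bound is 310/5 = 62 HU.

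**The case against.** The best defence has four parts.

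- **Pooling is not stated.** A reader might infer that the plan computes one coefficient over all arms. Section 13.4.4 is silent, and the general rule in section 13 points towards results by arm. This stands: the fault is an unspecified grouping, not a stated wrong one.
- **A high value is not assured.** A reader might also infer that the coefficient is bound to look good. The only numerical planning assumptions give an artefact of about 0.12. The figure of 0.84 needs all three arms apart, whereas section 10.1.1 likens both comparators to the wall, which favours 0.75 as the ceiling. This also stands. However, 1.50 and 2.00 carry no unit and fit poorly with gaps of hundreds of HU, so the larger values remain plausible.
- **Offset is already covered.** The signed rank test is there to find a systematic reader shift, and section 13.2 provides descriptive statistics and 95% intervals for continuous data. This stands in part. The test gives no size in HU and does not address random disagreement, and section 13.2 is not linked to reader differences.
- **The analysis is exploratory.** No threshold or success criterion depends on it. That limits the consequence, but section 6.2 still names repeatability as a secondary objective, and this is the only analysis offered for it.

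**Conclusion.** The point holds in a limited form. As written, the plan cannot report how far apart the two readers are in HU. That is true whether the Spearman coefficient is pooled or by arm, and it needs no assumption about the data.

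The second part is conditional. If the coefficient is pooled over 40:20:20 and within-arm reader correlation is zero, arm separation alone produces about 0.12 at 0.75 SD, 0.54 at 2 SD, 0.70 at 3 SD and 0.75 from about 5 SD. It produces 0.84 if all three arms separate fully. These values rest on normal data with equal SDs and on an assumed separation. The density gap described in sections 5.1, 5.2 and 7.3.1 makes the upper end plausible but does not establish it.

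The documents do not support the stronger conclusion that the primary comparison is compromised. The primary test uses the average over both readers and does not depend on section 13.4.4.

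**What to change.** In section 13.4.4, make the following the main reader analysis, by arm and on per-subject reader means. Subject means are the natural unit because the readers choose ROI sites separately.
- Mean reader difference in HU with 95% CI.
- Bland-Altman 95% limits of agreement, with a plot.

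Keep the signed rank test as supportive, and report any Spearman coefficient within arm only. An absolute-agreement intraclass correlation with CI is optional. In a homogeneous arm it can be low even when the readers differ by only a few HU, so it should not replace the limits.

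The cost is SAP wording, one table and one plot. Both readers' values are already entered in the eCRF.

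Intervals will be wide in the arms of 20. With s the SD of reader differences, the standard error of a limit is about s × √(1/n + 1.96²/(2(n − 1))). For n = 20 this is 0.389s, or ±0.81s with t = 2.093. For n = 40 it is 0.272s, or ±0.55s with t = 2.023. The primary analysis needs no change.
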